## 5.4 Exclusion Criteria

The following reasons will exclude subjects from registry participation:

- Subjects who cannot be reached by phone;
- Subjects who are unable to answer the registry questionnaires and who do not have a next of kin or caregiver available to answer the registry questionnaires;
- Subjects who – either during the lag interval or subsequently – enter an interventional study.

## 5.5 Study Region/Location

The registry will include the sites that participated in the Sponsor's oral cladribine clinical trials in MS, which include countries in North and South America, Europe, Africa, and Asian-Pacific regions.

Language, cultural and regulatory aspects of the potentially large number of participating countries will be taken into account during the planning phase of the registry.

## 5.6 Study Cohort

The cohort of cladribine-treated subjects will consist of all subjects who have consented to participate and who were treated with cladribine during the clinical trial period of the identified clinical trials or cladribine extension studies in MS.

There will be no control/comparison group. Subjects who were on placebo during a clinical trial but who switched to cladribine in the extension study will contribute person-time to the cohort of cladribine-treated subjects from the moment they initiate cladribine. Person-time prior to cladribine initiation in subjects originally randomized to placebo, will not be used in the calculation of study endpoints incidences.

## 5.7 Follow-up and Study Duration

### *Study duration*

Enrollment of subjects in the registry will start after subjects completed or discontinued participation in an oral cladribine clinical trial in MS. The end of the registry is planned for 2018, which corresponds to 8 years after the last subject was included in the targeted clinical trials (see section 5.1).

### *Follow-up of MS subjects*

*The duration of follow-up for all subjects will extend up to the end of the registry, which is planned for 2018, or 8 years after enrollment into the first cladribine clinical trial (first visit), whichever occurs first.*

*Subjects with ongoing SAEs, including lymphopenia (i.e. who have not reached a lymphocyte count CTCAE Grade 0 or 1) at the end of PREMIERE, will be followed-up by the Global Drug Safety department until resolution (see definition of the reporting period in section 8.5.1.5).*

### *Follow-up of offspring*

The duration of follow-up for offspring of female subjects born during registry participation or during the lag interval period will be one year after delivery or until the registry end date, whichever occurs first.

*Subjects with ongoing pregnancies or offspring born during registry participation or during the lag interval period who are not at least 1 year old at the end of the registry will be followed-up by*

the Global Drug Safety department until pregnancy outcome is known and offspring is 1 year old, respectively (see definition of the reporting period in section 8.5.1.5).

[figure not shown]
### 5.7.1 Study Termination

Termination of a subject from the registry will occur if the subject decides not to continue his/her participation in the registry or if the subject becomes unable to continue participating. Subjects will be informed that they have the right to withdraw from the registry at any time, without prejudice, and that they are not obliged to state their reasons. If a subject declares his or her wish to discontinue from the registry, the PRP will attempt to establish whether the underlying reason is related to an adverse event (AE) or other study endpoint. The PRP will complete a Subject Discontinuation form and enter the discontinuation information into the electronic case report form of the discontinued subject.

### 5.7.2 Lost to Follow-up

Before considering a subject “lost to follow-up,” the PRP or trained site personnel will make every attempt to contact the subject and maintain him/her in the registry and to ensure that an outcome of interest has not been the underlying reason for the non-response of the subject. If no response is obtained, the CRO will enquire directly with other known health care providers and/or with next of kin/caregivers named by the subject via PRP to check whether the reason for failure to respond is health-related, to determine the vital status of the subject, and, in the case of deceased subjects, to ascertain the cause of death.

Figure 1 Registry Overview Diagram

## 6 Study Endpoints

### 6.1 Primary Endpoints

- Cumulative incidence of SADR, including malignancies and serious infections
- Time to resolution of lymphopenia, among registry participants with persistent lymphopenia

- Cumulative incidence of all AEs in the “Blood and Lymphatic System Disorders” System Organ Class (SOC) and in the “Neoplasms Benign, Malignant, and Unspecified” SOC

## 6.2 Secondary Endpoint

- Pregnancy outcomes, including congenital malformations, spontaneous abortion, elective abortion, stillbirth, ectopic pregnancy, molar pregnancy, and other important health conditions in the offspring

## 6.3 Definitions related to study Endpoints

### Resolution of Persistent Lymphopenia

Subjects who complete or drop out of a cladribine clinical trial with a Grade 3 or Grade 4 lymphopenia as defined by the Common Terminology Criteria for Adverse Events (CTCAE) [8] will be defined as having ‘persistent lymphopenia’ and will be monitored until lymphopenia resolves. Resolution is the achievement of a CTCAE Grade 1 or Grade 0 lymphocyte count.

According to the CTCAE version 4.03 [8], lymphopenia grades are defined as follows:

- Grade 1: < lower limit of normal (LLN) to 800/mm^3 or < LLN to 0.8 × 10^9/L
- Grade 2: < 800–500/mm^3 or < 0.8–0.5 × 10^9/L
- Grade 3: < 500–200/mm^3 or < 0.5–0.2 × 10^9/L
- Grade 4: < 200/mm^3 or < 0.2 × 10^9/L

### Pregnancy and Pregnancy Outcomes

Pregnancies occurring among female subjects exposed to cladribine will be identified by a subject-reported positive pregnancy test and at least a 2-week delay in menses, or a subject-reported pregnancy diagnosed by a physician.

Pregnancy outcomes will be characterized by using the following definitions (in italics) according to the European Medicines Agency guideline [9].

#### *Live births*

*Complete expulsion or extraction from its mother of a product of conception irrespective of the duration of the pregnancy, which after such separation, breathes or shows any evidence of life.*

Normal

Abnormal:

Pre-term, term, post-term birth

*Pre-term birth: less than 37 completed weeks (less than 259 days) of gestation.*

*Term birth: from 37 to less than 42 completed weeks (259 to 293 days).*

*Post-term birth: 42 completed weeks or more (294 days or more)*

Small for gestational age infants/ intrauterine growth retardation

*Intrauterine growth retardation (small for gestational age): the observed weight of a live born infant or size of a fetus is lower than expected on the basis of gestational age.*

*Gestational age or length: the duration of gestation is measured from the first day of the last normal menstrual period. Gestational age is expressed in completed days or completed weeks (e.g., events occurring 280 to 286 days after the onset of the last menstrual period are considered to have occurred at 40 weeks of gestation).*

Drug withdrawal syndrome in the neonate

Malformations

Morbidity

### ***Fetal death***

*Death prior to complete expulsion or extraction from its mother of a product of conception, irrespective of the duration of pregnancy; the death is indicated by the fact that after such separation the fetus does not show any evidence of life. Early fetal death (before 22 completed weeks of gestation) comprises ectopic pregnancy and miscarriage.*

#### Ectopic

*Extrauterine pregnancy, early fetal death most often in the Fallopian tube.*

#### Miscarriage

*Spontaneous abortion, molar pregnancy.*

#### Stillbirth

*Late fetal death (after 22 completed weeks of gestation).*

#### Termination of pregnancy

*Induced abortion, elective abortion. Artificial interruption of pregnancy.*

In cases of induced or spontaneous abortions and intra-uterine death, it should be mentioned whether the embryo/fetus had apparent congenital malformations.

### **Major structural birth defects or genetic syndromes**

Descriptions of major congenital anomalies and congenital syndromes of offspring will be collected.

A simplified version of the British Pediatric Association code list will be used for the definition of this endpoint. See Section 13 [Appendix III](#).

### **Developmental disabilities and important health conditions**

Data on routine developmental milestones achievement and important health conditions as reported by a physician will be collected in offspring for the duration of follow-up (see Section 5.7).

## **7 Assessment of Medication Exposure**

After enrollment of subjects in the registry, in accordance with the non-experimental nature of this study, no treatment will be assigned to participants by registry protocol. Physicians will prescribe medications according to their own clinical criteria and practices. Information regarding use of marketed immunosuppressant medications will be collected during the registry.

Subjects will no longer be eligible to participate in PREMIERE if they enroll in an interventional clinical trial, as it may not be possible to know medication exposure.

### **7.1 Prior Exposure to Cladribine**

Data on the subject's prior exposure to cladribine from the clinical trial period will be copied from the clinical trial database and will include the following variables:

- Date of cladribine start;
- Cumulative cladribine exposure (mg per kg of body weight)
- Dose and schedule;
- Date(s) of temporary and/or permanent treatment discontinuation(s).

## **8 Data sources and Study Procedures**

Subjects will be provided information on the registry and will be requested to sign informed consent before any data is collected.

For subjects who refuse to enroll in the registry, attempts will be made to collect selected data, including reason for refusal, and to request informed consent for the use of their baseline data collected during their participation in the clinical trial.

When a subject has signed the informed consent, a unique subject identification number will be assigned. This number will consist of ten characters for the registry protocol number, three digits for a site number and four digits for a sequentially assigned subject number (i.e., 0001, 0002, 0003, etc.).

**Example:** the fifth subject enrolled at site 001 in protocol 0700568012

0700568012	001	0005
Protocol No.	Site No.	Subject No.

Should the subject withdraw from the study, his or her unique subject identification number will not be reallocated.

## 8.1 Data Sources

Data will be obtained from several sources, namely:

The subject questionnaires administered by the PRP or trained site personnel

- Medical record information collected by the PRP at his or her own institution providing information on subject health events and exposure to other immunosuppressants
- The clinical trial database, providing data previously collected during the oral cladribine clinical trials in MS and their extension

The specifics of these data sources are described in the following paragraphs.

### Subject Interviews

After registry enrollment, data will be collected by the PRP or trained site personnel (see Section 13 [Appendix I](#), schedule of Interviews) either during the routine clinical visit or by telephone contact. Structured questionnaires administered to the subject or in cases when the subject is unable, to the next of kin, or caregiver.

There will be a limited number of subjects who withdrew or completed the clinical trial before the registry was established and who have no follow-up data recorded in their medical record (or the medical record is not accessible). Information from this time interval between clinical trial end and registry enrollment, referred to as the “lagged data period,” will be collected directly from the subject. As much as possible medical confirmation will be sought through the PRP.

### Medical Records

For subjects who withdrew or completed the clinical trial before the registry was established (but who are still followed at the site), health records will be retrospectively reviewed to ascertain SADRs, pregnancies, and lymphocyte counts, as well as exposure to immunosuppressants occurring during the lagged data period.

### Clinical Trial Database

Data collected from the clinical trial period will include demographic characteristics, exposure to cladribine and lymphocyte counts at the end of the trial. This data will be linked with the clinical trial data after enrollment of the subject in the registry.

## 8.2 Schedule of Interviews and Subject Questionnaires

### Timing and Frequency of Interviews

On Day 1 of registry enrollment, the interviewer (PRP or trained site personnel) will verify that the informed consent has been signed and will proceed to administer the registry enrollment questionnaire.

During the first 2 years after enrollment into the registry the PRP or trained site personnel will interview the subject every 3 months. Thereafter, the contacts will be every year until the end of follow-up (see Section 13 [Appendix I](#), schedule of Interviews).

A window of  $\pm 2$  weeks around the date of the scheduled visit during the first two years and of  $\pm 4$  weeks thereafter, is acceptable. The structured questionnaire will be administered during routine clinical visits or by phone. The PRP or trained site personnel will enter the questionnaire responses collected in the electronic case report form. The completed questionnaires are source documents and will be filed with the registry participant's medical records on site, per Section 11.4 of the protocol.

At each scheduled contact, information on SAEs, AEs related to 'Blood and Lymphatic System Disorders' and 'Neoplasms Benign, Malignant, and Unspecified' SOCs, lymphocyte counts, and immunosuppressant medications will be collected through a structured questionnaire administered by phone or during a routine visit by the PRP or trained site personnel. A detailed schedule of interviews is provided in the Section 13 [Appendix I](#), schedule of Interviews.

**Pregnancies:** When a pregnancy is identified in a female subject, a specific pregnancy baseline questionnaire will be administered (see Section 8.3). During the pregnancy, the schedule of phone interviews will be adapted so that at least one such interviews takes place between months 4 through 7 after the last menstrual period (LMP), and another at month 10. After the end of the pregnancy, the schedule of interviews will shift to the regular periodicity.

**Offspring of female subjects:** *Data will be collected from the PRP after birth, ideally in parallel to the interview of the mother at month 10 post-LMP, at age 6 months, and at age 1 year. No interviews on the offspring will be performed in the frame of the registry after the date of the registry end. Offspring who are not at least 1 year old at the end of the registry will be followed-up by the Global Drug Safety department (see definition of the reporting period in section 8.5.1.5).*

A schedule of interviews for pregnancies and offspring is provided in Section 13 [Appendix II](#), Schedule of Interviews for Pregnancies and Offspring.

To manage missed interviews or shifts in scheduled interviews of subjects, the registry will maintain the schedule as originally planned.

## 8.3 Baseline Subject Demographic and Other Characteristics

The registry enrollment of a subject will be based on subject interview and, for some subjects, will require information from subject health records. Another component of the enrollment process will consist of inclusion of data collected during the clinical trial period, which will be copied from the

clinical trial database to the registry database after completion of the subject enrollment into the registry.

### **8.3.1 Registry Baseline Data Elements**

Registry baseline data elements include the following data:

#### **8.3.1.1 Information from registry enrollment interview**

At the registry enrollment interview, the following data will be collected from all subjects unless prohibited by country regulations:

- Identification/contact information of subject, next of kin/caregiver, and current treating physician(s).

In subjects who have a lagged interval period and whose medical record is not accessible, a specific questionnaire will address the following:

- Treatment exposure to immunosuppressant medications, including type of treatment and date started;
- Occurrence of SAEs including time and outcome;
- Occurrence of AEs in the ‘Blood and Lymphatic System Disorders’ and ‘Neoplasms Benign, Malignant, and Unspecified’ SOCs including time and outcome
- In subjects tagged as “lymphopenic subjects” ascertainment of performance of a blood test during the lagged data period, and categorization of lymphocyte counts as normal, abnormal or unknown, if available.

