#### **8.3.1.2 Information from medical health records review**

For subjects with lagged data period, Sponsor will review data from medical records and the PRP will enter the following data into the registry participant electronic case report form:

- Treatment exposure to immunosuppressant medications, including type of treatment, and date started;
- Occurrence of SAEs including time and outcome;
- Occurrence of a pregnancy in participant woman, including date of LMP, and outcome;
- In subjects tagged as “lymphopenic subjects” ascertainment of performance of a blood test during the lagged data period, and categorization of lymphocyte counts as normal, Grade 1 through Grade 4 or unknown, if available.

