In this protocol, any adverse pregnancy outcome (e.g., spontaneous abortion, fetal death in utero, ectopic pregnancy, chronic fetal distress, stillbirth, neonatal death, or prematurity-related complication more than is typical for prematurity) should be considered serious. Serious adverse events occurring to offspring of a female subject should also be reported and evaluated as SAEs.

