Secondary			

 To assess pregnancy outcomes, including congenital malformations or other important health conditions in the offspring born to women exposed to oral cladribine 	
 Pregnancy outcomes, including congenital malformations, spontaneous abortion, elective abortion, stillbirth, ectopic pregnancy, molar pregnancy, and other important health conditions in the offspring 	
 Number of patients with pregnancies from Registry Day 1 to End of registry and descriptive statistics of pregnancy outcomes 	
 Section 15.2

6 Overview of Planned Analyses

Summary of PREMIERE registry

The PREMIERE study is an ongoing prospective observational long-term safety registry of patients who have participated in at least one of the 5 cladribine clinical trials (namely CLARITY [25643], CLARITY EXT [27820], ONWARD [26593], ORACLE [28821] and the pantoprazole drug-drug interaction [DDI] phase I study [27967]). These 5 studies are referred throughout this document under the general term "clinical trials".

The original objectives of the PREMIERE registry were to monitor long-term safety events in a clinical trial population to produce long-term safety data in order to better characterize the potential safety risks of oral cladribine, and to build an evidence-based risk minimization strategy. The study was amended with simplification and including restriction to serious adverse drug reactions (SADR), selected AEs (all AEs in the 'Blood and Lymphatic System Disorders' and 'Neoplasms Benign, Malignant, and Unspecified' SOCs) and reduction of frequency of assessments. The duration of follow-up in the registry is up to the end of the registry or 8 years after the subject's first enrolment into a cladribine clinical trial, whichever occurs first. Last patient last visit for the final analysis was on October 25th, 2018.

[figure not shown]

Figure 1 PREMIERE Registry Overview Diagram

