9.4 Dictionary coding

The Adverse events (AEs) and Medical History will be coded to MedDRA version 21.0. Concomitant medications will be upgraded with WHO Drug Dictionary version March 2018 (WHODRUG B2 MARCH2018).

9.5 Study Day 1

Study Day 1 is the day of start of first study drug intervention (placebo or cladribine). For patients in the sequence placebo-cladribine, the placebo period is ignored and Study Day 1 is at the start of cladribine. The day before is Study Day -1 (no Study Day 0 is defined).

9.6 Registry Day 1

Registry Day 1 is defined as the end of clinical trial +1 day. The day before is Registry Day -1 (no Registry Day 0 is defined).

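### The lag questionnaire for subjects without accessible records lists no pregnancy item, so among pregnancies that ended before enrollment only adverse outcomes have a prompted route into the SAP's counts

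*Protocol*

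**What the plan says.** The protocol gives two ways to recover events from the interval between trial end and registry enrollment.

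- **Records accessible.** Protocol 8.1 (Medical Records) says that "health records will be retrospectively reviewed to ascertain SADRs, pregnancies, and lymphocyte counts". Section 8.3.1.2 then lists, among its items, "Occurrence of a pregnancy in participant woman, including date of LMP, and outcome".
- **Records not accessible.** Protocol 8.3.1.1 says: "In subjects who have a lagged interval period and whose medical record is not accessible, a specific questionnaire will address the following". The list that follows has four topics: immunosuppressant exposure; "Occurrence of SAEs including time and outcome"; adverse events in the blood and neoplasm organ classes; and, in subjects tagged as lymphopenic, blood tests and lymphocyte status.

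Protocol 8.5.1.3 states that "any adverse pregnancy outcome (e.g., spontaneous abortion, fetal death in utero, ectopic pregnancy" and similar events should be treated as serious. Elective termination is not among its examples, but Protocol 6.2 lists it as an outcome of the secondary endpoint.

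The SAP's objectives table (section 5) sets the time frame for that endpoint as "Number of patients with pregnancies from Registry Day 1 to End of registry and descriptive statistics of pregnancy outcomes". SAP 9.6 fixes the start: "Registry Day 1 is defined as the end of clinical trial +1 day".

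**The concern.** The two lists serve the same purpose for the same interval, yet only one asks about pregnancy. If the omission led only to fewer pregnancies being counted, the result would be incomplete but not necessarily skewed. Here the loss depends on the outcome. Women who had a miscarriage, ectopic pregnancy or stillbirth in the interval are prompted through the serious-event question; women who had a healthy child are not.

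At stake are the outcome proportions of the only secondary endpoint, in a registry set up partly to learn about reproductive safety. The number of pregnancies is likely to be small, so a few unrecorded normal births would show in the table.

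**Working it through.** **Step 1. Look for another specified route for a completed lag-interval pregnancy in a woman without accessible records.**

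| Provision | What it covers | Closes the gap? |
|---|---|---|
| Protocol 8.5.3.1, mandatory pregnancy recording | Conceptions in the 8.5.1.5 reporting period, which starts at consent | No |
| Protocol 8.5.1.5, lag-interval rule | Serious events the reporter becomes aware of | Adverse outcomes only |
| Protocol 8.3.1.4, pregnancy baseline questionnaire | Women who become pregnant during registry participation | Only incidentally, as obstetrical history in a later pregnancy |
| Protocol 8.4, follow-up interview categories | Contacts, serious events, two organ classes, lymphocytes, immunosuppressants | No |
| Protocol 8.5, interview prompt | Pregnancy is elicited at interviews after enrollment | Probably for a pregnancy ongoing at enrollment; no look-back specified for one already ended |
| Protocol 5.7, offspring follow-up | Includes children born in the lag interval | States an intention; names no step to identify these births |
| SAP 15.2, data sources | Any dataset holding pregnancy data, including adverse event reports | Uses what was collected; does not collect more |

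Adverse outcomes therefore have a prompted route. Normal births, and probably elective terminations, have none.

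**Step 2. Confirm that the SAP includes this time.** Registry Day 1 is the day after trial end, and enrollment comes later for lagged subjects. The whole lag interval is inside the counting window, and SAP 15.2 does not separate it.

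**Step 3. Illustrate the size.** The plan states no figure to reproduce. The inputs are the CLARITY pregnancies in Protocol section 3: 5 normal live births, 13 elective abortions, 1 therapeutic abortion for choriocarcinoma, 4 miscarriages and 1 ectopic pregnancy, so 5 + 13 + 1 + 4 + 1 = 24.

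- Outcomes that would surface as serious events: A = 4 + 1 + 1 = 6.
- Outcomes without a prompted route: N = 5 + 13 = 18.
- True adverse share: 6/24 = 25.0%.

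Let f be the share of pregnancies that fall in the unasked group. The documents do not give f, so it is assumed. If all adverse outcomes are captured and none of the others in that group are,

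observed share = A / (A + N × (1 − f)).

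| Assumed f | All outcomes (A = 6, N = 18) | Without elective abortions (A = 6, N = 5) |
|---|---|---|
| 0% | 6/24 = 25.0% | 6/11 = 54.5% |
| 5% | 6/23.1 = 26.0% | 6/10.75 = 55.8% |
| 10% | 6/22.2 = 27.0% | 6/10.5 = 57.1% |
| 20% | 6/20.4 = 29.4% | 6/10 = 60.0% |
| 50% | 6/15 = 40.0% | 6/8.5 = 70.6% |

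For any given f these figures are the extreme case. If some adverse outcomes also go unreported, or some normal births are volunteered, the shift is smaller.

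**The case against.** Several points on the other side stand.

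- **The group is narrow.** Protocol 8.1 (Subject Interviews) opens its description with "There will be a limited number of subjects who withdrew or completed the clinical trial before the registry was established" and narrows it further to those with no recorded follow-up or no accessible record. Only women count, and mainly pregnancies that ended before enrollment.
- **Unprompted capture is possible.** Protocol 5 and 8.1 intend lag-interval information to be collected from the subject, with medical confirmation sought where possible. The pregnancy term list in SAP Appendix 18.1 includes live birth and induced abortion, so a volunteered report would be used. The lag form itself is not in the documents and may ask more than 8.3.1.1 lists.
- **The endpoint is descriptive.** No inference is planned, and SAP 15.2 provides a listing of pregnancy details, so timing can be checked case by case.

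These limit the size of the problem but do not restore symmetry between outcomes.

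A reader might also infer that the gap falls where it matters most, because SAP 15.2 separates pregnancies starting within 183 days of the last dose and the lag interval seems closest to treatment. The documents do not support that. The lag begins at the last trial data collection (SAP 9.8), not at the last dose. In CLARITY, retreatment was at Weeks 48 and 52 (Protocol section 3). Counting from Week 52, day 364 + 183 = day 547, about Week 78; adding a 28-day course gives day 575, about Week 82. The SAP's lymphocyte windows run to Week 96 and beyond. Trial length is not stated outright, but this suggests that the six-month window mostly closed inside the trial for CLARITY completers. Early dropouts may differ, and the documents do not give the corresponding timing for the other trials.

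**Conclusion.** The point holds as a gap in the protocol's specification. For lagged women without accessible records, a pregnancy that ended before enrollment has a prompted route only if its outcome was adverse, and the SAP counts that interval without distinguishing it. The bias in outcome proportions is towards adverse outcomes.

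The overall effect is probably modest. On the CLARITY mix with 5% to 10% of pregnancies affected, the adverse share rises from 25.0% to 26.0% to 27.0%. This rests on an assumed f, on the CLARITY mix carrying over to the registry, and on full capture of adverse outcomes with no capture of the others. The documents allow neither f nor the affected group to be sized.

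A reader might conclude that normal births in this group were simply lost, so that its adverse share would read 100%. The text shows only that no pregnancy prompt is listed; it does not show that nothing was captured.

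**What to change.** Add to the Protocol 8.3.1.1 list the item that 8.3.1.2 already has: occurrence of pregnancy, date of last menstrual period, and outcome. This costs one questionnaire item.

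SAP section 6 gives the last visit as 25 October 2018, so for this registry the practical change is in SAP 15.2:

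- Flag each pregnancy that ended between trial end and enrollment, with its data source (records review, lag questionnaire, adverse event report, other).
- Keep the full pregnancy table as the main display and add the lag-interval pregnancies as a separate tabulation by source, as a sensitivity display.
- State in the report that lag-interval pregnancies in women without accessible records were not systematically asked about, and give the number of such women.

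Known lag-interval pregnancies should stay in the main table; removing them would discard reported adverse outcomes in a safety registry. The cost is one derived flag, one extra table and a limitation statement. The documents do not show that a source variable exists. If it does not, the flag has to be derived from the dataset of origin, pregnancy dates and enrollment date, or assigned by reviewing the planned listing.
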